In 2023, the ESCP conducted an international survey on common practices in abdominal wound closure and SSI prevention. (23) Over 500 ESCP members, colorectal and general surgeons participated in this study. Three common clinical scenarios were described, which included contaminated emergency surgery, clean contaminated laparoscopic and open surgery. Participants were asked to indicate how they would approach each case. The study found significant heterogeneity in common practices for abdominal wound closure and SSI prevention, including various types of fascial closure techniques and sutures used, skin preparation and sterility measures taken during the surgical intervention. This cohort study, and the parallel audit, will be the first large scale international study to investigate the impact of wound closure and early wound complications on the long term outcomes.

Justification of patient population

There are few prospective studies on variations of practice worldwide. Randomised studies on abdominal wound closure often focus on general and clean or clean-contaminated surgery, in absence of ostomies. Whether abdominal wound closure strategies can be fully extrapolated to colorectal surgery patients is questionable. This study will provide data on patients who are infrequently included in randomised studies, such as patients who undergo emergency surgery and dirty surgery. In addition, the study will provide the surgical community with data regarding global heterogeneity in the uptake of various recently proposed innovations including the small bites technique, and prophylactic mesh in colorectal surgery, as well as provide contemporaneous operative outcomes on an unselected population.

Rationale for study design

Cohort studies allow for the gathering of large numbers of unselected patients from many hospitals over a relatively short timeframe. There are two components to WOLVERINE that are being conducted: the WOLVERINE COHORT study, detailed within this protocol, and the WOLVERINE AUDIT, detailed in a separate protocol. Patient eligibility is the same within each study.

The cohort study will provide contemporaneously collected data on the impact of wound infection or long term wound failure on quality of life. This cohort study will also be the first study to collect and link data on short-term wound healing issues with longer-term wound failure.

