The parallel prospective audit study will result in the generation of a large, international dataset of real-world data on wound closure and SSI prevention practices for patients undergoing abdominal surgery, and enable the first description of the global variability in practice.

This dataset will be used to explore how differences in patients, treatment practices and preventative measures may be associated with different clinical and patient-reported outcomes. The datasets will be analysed separately. They cannot fully control for selection bias and interaction effects; as such, they create hypothesis-generating information rather than true evidence of effect. The data collected as part of this study will be used to inform the design of a future interventional study on abdominal wound closure and SSI incidence in the elective and expedited/emergency general and colorectal surgery patient populations.

AIMS & OBJECTIVES

Main research question:

1. What is the relationship between differing wound closure materials and techniques, with the occurrence of early and late abdominal wound failure?

Abdominal wound failure includes surgical site infections according to Center for Disease Control classification, surgical site occurrences (which will be described excluding SSI,

Wolverine Protocol IRAS: 334321 version 1.0 dated 30 January 2024

abdominal wound dehiscence), abdominal wound dehiscence with or without evisceration, and incisional hernia formation. (24) Abdominal wound dehiscence (also referred to as 'evisceration' or 'fascial dehiscence') is an unintended acute wound failure at the level of the fascia and is a postoperative complication after primary closure of a laparotomy incision. (25) Incisional hernia is an example of late abdominal wound failure, occurring up to 65% in high-risk groups and up to at least 10 years after surgery (*long term follow-up of the PRIMA trial, accepted for publication in the Lancet.* (26) It was defined by the European Hernia Society as "any abdominal wall gap with or without a bulge in the area of a postoperative scar perceptible or palpable by clinical examination or imaging". (27, 28)

Further research questions:

- 1. What is the relation between early abdominal wound failure and late abdominal wound failure?
- 2. What is the impact of late abdominal wound failure, including incisional hernia, on the patient's quality of life?
- 3. What are the rates of early and late abdominal wound failure?

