- 4. What are the effects of SSI prevention measures on the incidence of early and late abdominal wound failure?
- 5. What is the impact of a minimally invasive technique vs. open technique on the incidence of early and late abdominal wound failure?
- 6. What is the impact of early and late abdominal wound failure on the patient?
- 7. What is the impact of early and late abdominal wound failure on the duration of postoperative stay and the number of outpatient visits and unscheduled hospital visits?
- 8. What are the early and late abdominal wound failure associated costs (eg, hospital/ICU stay, unscheduled hospital visits and patient reported expenses)?
- 9. Which risk scores will have the highest predictive value for our primary outcomes within this cohort?

Summary of the cohort study key objectives

Short term:

Assessing the different practices of wound closure and surgical site prevention globally

Assessing the effect of wound closure and surgical site infection prevention practices on the incidence of abdominal wound failure at 30 days.

Longer-term:

Early phase: 30 days to 90 days
Assessing the different practices of abdominal wound closure and surgical site prevention globally and their effect on wound healing, SSI, patient recovery and return to normal function.

Later phase: 90 days to 1 year
The incidence of abdominal wound failure, including the development of incisional hernia.

Overall:

Exploring the relationship between early adverse wound outcomes and longer-term patient-reported incisional hernia occurrence.

Comparison of quality of life for patients with and without wound healing issues and/or incisional hernia.

Key outcome measures

Short term:

Methods of Wound Closure:

- Types and techniques of fascial, subcutaneous and skin closure
- Incidence and types of mesh use
- Use of SSI Prevention measures
- Incidence of abdominal wound failure at 30 days
- Length of postoperative stay
- Reoperations within 30 days
- 30-day mortality
- SSI diagnosis or management requiring ICU admission
- Unplanned readmissions within 30 days
- Need for interventional radiology procedures within 30 days
- Abdominal wound dehiscence within 30 days

Long-term:

Patient-reported outcomes and quality of life from 30 days to 1 year post-operation

At all time points:

- EQ5D-5L
- SF-12

Early phase [wound healing / SSI / return to normal function]: 30 days to 90 days

- Bluebelle wound healing questionnaire at 30 days

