- Patient reported Wound Recovery PROM - outpatient visits, unplanned hospital visits within 90 days, wound healing, return to work, satisfaction with wound at 30 days
- Repeat the Patient reported Wound Recovery PROM at 60 days and 90 days if wound is not fully healed at these time points

Late phase [wound integrity, reintervention, incisional hernia]: 90 days to 1 year

- Clavien Dindo classification at 30 days
- Surgical site occurrences at 30 days
- ESCP Incisional hernia PROM at 90 days, 6 months, 1 year
- HerQles questionnaire at 1 year

STUDY DESIGN

International prospective cohort study.

The study will collect wound closure and SSI prevention measures employed, and short-term clinical outcomes up to 30 days and longer-term patient-reported outcomes.

Study Timelines

- The cohort study, will open within one month of being approved.
- Participating sites must have started recruitment within 3 months of the study being approved.
- The study is anticipated to close to recruitment in mid-2025.

ELIGIBILITY

Hospital inclusion criteria

Any hospital or surgical unit performing elective and/or emergency abdominal general and colorectal surgery.

Participating sites will be expected to recruit at least 10 consecutive eligible patients within a 4-week period.

At hospital level, data completeness of 95% will be required.

Patient eligibility

Inclusion criteria

- Adult patients (age 18 years and above) undergoing general or colorectal surgical procedures
- Elective (planned admission), expedited (within two weeks), or emergency (unplanned admission) surgery.
- General and colorectal procedures using any type of abdominal incision measuring at least 5 cm (including extraction sites).
- Able to give written informed consent

*For those patients who do not speak the national language of the country in which they are recruited for participation, normal hospital policies for translation to facilitate participation will be followed.

Exclusion criteria

- Patients undergoing incisional, ventral, umbilical, and inguinal/femoral hernia repair
- Simultaneous hyperthermic intraperitoneal chemotherapy (HIPEC) and/or cytoreductive surgery
- Stoma reversal without additional laparotomy incision
- Anyone who does not have an email address or who does not have access to the internet or a smart device.

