Note: Each individual patient should only be included once. Following the index procedure (i.e. the procedure for study inclusion), patients undergoing additional procedures within the study window should not be included for a second time. Data on these additional procedures will be captured as part of patient follow-up.

Selection bias

Selection bias will be closely monitored by the Study Management Group. Study coordinators will regularly liaise with site Principal Investigators to ensure that all eligible patients are entered consecutively into the study. Recruitment rates will be monitored across individual sites and clarification will be sought in case of a drop in recruitment that might indicate that eligible patients were not included.

PATIENT IDENTIFICATION AND CONSENT

All consecutive adult patients who fulfil the eligibility criteria should be included. As this is an international study, each participating country and hospital will decide how best to identify and approach eligible patients. It is anticipated that potential participants may be identified as described below.

Potential participants may be identified:

- Pre-operatively:
 - Surgical outpatient clinics (e.g. when the patient is being booked for elective surgery)
 - Planned theatre lists (e.g. at the time of admission for surgery)
 - Emergency surgical admissions (e.g. at the time that a decision to operate is made)
- Intra-operatively
 - By operative team
- Post-operatively prior to discharge:
 - By the operating surgeon

SCREENING

The WOLVERINE Screening Log will be held on the REDCap data capture system. Each potential participant will be recorded by the site and a REDCap id number generated for every record entered. This REDCap ID number will then be used for those patients who are eligible and provisionally agree to enter the cohort study.

No specific screening visits or other screening procedures are planned.

INITIAL APPROACH TO PATIENT

Potential participants will be approached by either:

- The senior operating surgeon
- Any doctor involved in the patients' care (e.g. surgeon in training)
- Clinical nurse specialist (depending on local regulations)

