The patient will be provided with a unique patient identification number by the person discussing the study with them (this is taken from the site-specific WOLVERINE REDCap LINK SHEET provided by the study office). This unique identifier will be recorded on the WOLVERINE PIS. Eligible patients will also be provided with a generic QR code. This QR code and unique identifier will be used by the potential participants to access the REDCap-WOLVERINE system and the consent form.

The potential participant will then be asked to access the online system at a time convenient to them, i.e. they do not need to access the system whilst in hospital. Upon access of the online REDCap system, they will be asked for consent for follow-up.

This unique REDCap ID will be the only identifier used to identify the patient in any correspondence between the coordinating centre and the participating site.

*Participating sites may download the consent form as a PDF if required for the WOLVERINE Site File.

STUDY FOLLOW-UP

Follow-Up Time points

After the baseline visit, there are no further study-specific visits. All study-specific follow-up is conducted via remote reporting.

There are 5 follow-up time points: 30-, 60- AND 90-days post-surgery; 6 months and one year post-surgery.

Short-term follow-up: 30-days post-surgery

- Clinician reported:
 - o Conducted without the need for patient attendance.
 - No specific follow-up visit is mandated for participants.
 - The 30-day post-surgical outcomes form is undertaken by the clinical team, with routinely collected information from patient notes or electronic records, or other routinely collected data sources.
- Patient reported
 - Data is collected remotely from the participant via the WOLVERINE online REDCap system
 - Bluebelle wound healing questionnaire, EQ-5D5L, SF-12, the Patient reported Wound Recovery PROM QoL and the ESCP Incisional Hernia PROM.

Longer-term follow-up

At the 60-days, 90-days, 6-month and 1 year post-operative timepoints, data is collected remotely from the patient only. The following questionnaires will be requested:

- The EQ-5D5L and the SF-12 at each of the 4 timepoints.
- Bluebell wound healing questionnaire at 30 days.
- Patient reported Wound Recovery PROM at 60 days and 90 days.
- ESCP incisional hernia PROM at 3-, 6- and 12-months.
- HerQles questionnaire at 1 year

^{**}There is no clinical team involvement beyond 30-days post-surgery.

COHORT STUDY SCHEDULE OF EVENTS

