patients will be followed-up to a maximum of 30-days postoperatively (with Day 0 being the day of surgery) by a review of their inpatient health records, routine clinic visit notes/letters, and reports for postoperative radiological investigations arranged as part of normal patient care. The study is designed efficiently so that existing patient follow-up pathways and health records can be used, with only data that is routinely collected as part of normal clinical care being captured.

Patient reported outcomes.

After completing informed consent, the patient will be sent a link by email, mobile phone or text to report outcomes in REDCAP. Consent for the cohort study can be obtained either before or after surgery, unless local ethics guidance stipulates otherwise.

DATA HANDLING AND RECORD KEEPING

Source Data

Source data within the study will be kept as part of the participants' medical notes generated and maintained at site. As all clinical data collected and analysed within the study are routinely gathered in clinical practice, source data will be within the medical notes.

The patient-completed questionnaires form source data. As these are completed online via the WOLVERINE REDCap database, this data will form part of the source data.

Data Management

Information will be collected at the following times:

- At baseline (surgeon level)
- At 30 days after the operation (surgeon level)
- At 30 days after the operation (patient level)
- At 60 days after the operation (patient level)
- At 90 days after the operation (patient level)
- At 6 months after the operation (patient level)
- At one year after the operation (patient level)

Data will be entered directly onto the secure electronic REDCap database by members of the research team and by participants.

Site study collaborators will be provided with a paper copy of the eCRF to facilitate data collection. If this is used, they should then transfer data from the paper CRF into the online database (https://www.bistc.redcap.bham.ac.uk). Data management staff will check all incoming data CRFs for completeness, data consistency and compliance with the protocol. If discrepancies or missing data are identified, the data management staff will raise queries with the research team at the participating hospital via the study database.

Data Security and Data Protection

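### Consent may be completed after surgery with no latest day, so 30-day mortality computed in consenters would be too low and early wound failure distorted in an unknown direction; the protocol does not settle which denominator applies

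*Protocol*

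**What the plan says.** **Entry.** Under Data management (Patient reported outcomes), "Consent for the cohort study can be obtained either before or after surgery, unless local ethics guidance stipulates otherwise". Under Process for consent for follow-up, patients consent online when it suits them, and "they do not need to access the system whilst in hospital". The latest stated point for identifying a patient is "Post-operatively prior to discharge". That limits identification, not the completion of consent. Identification before surgery is described only as ideal. Ability to consent is an inclusion criterion, and the exclusions add "Anyone who does not have an email address or who does not have access to the internet or a smart device".

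**Outcomes.** Key outcome measures (Short term) lists "30-day mortality", reoperations within 30 days and abdominal wound failure at 30 days. Further research question 3 asks for the rates of early and late failure. Clinician follow-up counts from day 0, the day of surgery. The Analysis plan summarises clinical outcomes in both the audit and the cohort populations.

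**Claims about the population.** Justification of patient population says that the study will describe emergency and dirty surgery, "as well as provide contemporaneous operative outcomes on an unselected population". Rationale for study design adds "Patient eligibility is the same within each study" and "The datasets will be analysed separately".

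**Text pointing the other way.** The synopsis attaches consent to the patient-reported component. Patient consent describes the clinician's baseline and 30-day data as routine and anonymised, and seeks consent for the patient-reported follow-up. The Schedule of events labels the clinician rows as audit data on all patients and only the patient-reported rows as limited to those who consent.

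**The concern.** A patient who dies before completing a post-operative consent can never join the consented cohort, while everyone who does join is counted as alive from day 0. In that group 30-day mortality is therefore understated by construction (immortal time). Patients who are in intensive care or too ill to go online may also be missed. A patient who consents late already knows how the wound is healing, so the decision to join can depend on the outcome.

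The loss would probably be greatest in emergency and dirty surgery, where there is least time to consent beforehand and which the study particularly wants to describe. The Background section says that the data will serve as a benchmark for a future interventional study. A rate carried forward from consenters alone could mislead its design.

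The stated safeguards do not address this. The Selection bias section monitors consecutive entry and drops in recruitment. The censoring weights in the Analysis plan deal with loss after entry, not with failure to enter.

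**Working it through.** **The plan's own figures.** The protocol gives no event rate, no share consenting after surgery and no timing of deaths. Its only number is an expected 1,000 patients, from feasibility, which implies about 1,000 / 10 = 100 sites at the minimum of 10 each. No rate can be reproduced, so what follows is a sensitivity calculation on assumed inputs.

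**Mortality among consenters.** Let m be true 30-day mortality, f the share who would consent after surgery, and q the share of 30-day deaths in that group that occur before consent is completed. Assume that consent is otherwise unrelated to outcome. Deaths retained are m(1 − fq) and patients retained are 1 − fqm, so

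observed = m(1 − fq) / (1 − fqm).

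This is below m whenever f and q both exceed zero, and equals m when f = 0.

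| m | f | q | observed | relative shortfall |
|---|---|---|---|---|
| 6% | 0.4 | 0.3 | 0.06 × 0.88 / 0.9928 = 5.32% | 11.4% |
| 6% | 0.6 | 0.5 | 0.06 × 0.70 / 0.982 = 4.28% | 28.7% |
| 3% | 0.8 | 0.7 | 0.03 × 0.44 / 0.9832 = 1.34% | 55.2% |

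The first and last rows are the extremes over m = 3-6%, f = 0.4-0.8 and q = 0.3-0.7. Defining f as the share of enrolled rather than eligible patients changes the extremes only to 11.5% and 55.5%.

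**Against sampling error.** With 1,000 patients and a 6% rate, the 95% half-width is 1.96 × √(0.06 × 0.94 / 1000) = 1.47 points. The bias in the middle row is 6.00 − 4.28 = 1.72 points, so it can exceed the random error.

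**Early wound failure.** Let w be the true rate and r the probability of consenting with wound failure relative to without, among those asked after surgery. With R = (1 − f) + fr,

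observed = wR / (wR + 1 − w).

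For an assumed w = 20%:

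| f | r = 0.5 | r = 1 | r = 1.5 |
|---|---|---|---|
| 0.5 | 15.8% | 20.0% | 23.8% |
| 1 | 11.1% | 20.0% | 27.3% |

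The direction depends on r, which the protocol does not give.

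**Which denominator applies.** Two readings are available.
- *Consenters:* the protocol says that it covers the cohort only, its eligibility criteria include consent and internet access, the 30-day outcomes stand among its key measures, and a cohort-population summary is planned.
- *All patients:* the Schedule of events and the Patient consent section tie the clinician 30-day data to everyone.

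On the second reading the consent mechanism does not affect the 30-day rates. The text does not choose between them.

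**The case against.** The strongest reply is that the clinician's 30-day data need no consent and cover all patients, so the rates escape this selection. The audit population is also to be summarised, and the Introduction says that cohort data will be used in combination with the audit findings. This stands as far as it goes: nobody can say that every reported 30-day rate will be biased. It does not settle the matter, because the all-patient rows are labelled audit, the audit has its own protocol, the two datasets are to be analysed separately, and a cohort-population figure is still planned.

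A reader might also infer that early wound failure is underestimated in the same way as mortality. The protocol does not support that. Very ill patients may be missed, but patients with wound trouble may be keener to join.

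A reader might further conclude that audit and cohort eligibility differ. The audit protocol is not at hand, so all that can be said is that the statement of identical eligibility fits poorly with consent and internet criteria when the audit takes only anonymised clinician data.

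Finally, the protocol concedes that selection bias cannot be fully controlled and calls its results hypothesis-generating. That caveat is fair but general. It does not mention survival to consent, and it sits beside the claim of an unselected population.

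**Conclusion.** The concern holds in a limited form. For any 30-day mortality figure computed in consented patients, the downward bias follows from the design as soon as one patient dies before completing post-operative consent. Early wound failure in the same group is open to selection of unknown sign. The range of about 11-55% for mortality rests wholly on the assumed inputs above. It shows that the bias could matter beside the sampling error, and it is not an estimate for this study.

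The defect in the text is that the denominators of the 30-day outcomes conflict between sections, while the cohort is presented as unselected although entry requires consent and an internet connection. Settling this changes what the study can conclude about early outcomes.

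**What to change.** 1. State that 30-day mortality, reoperation and early wound failure rates are estimated from the clinician-reported records of all eligible patients (the audit rows or the screening log), not from consenters only. Reconcile the synopsis, Key outcome measures, Schedule of events and Analysis plan accordingly.
2. Record the date of consent relative to surgery. Present any cohort 30-day figure as conditional on consent, with pre-operative consenters as a sensitivity analysis.
3. Tabulate consenters against all eligible patients on the shared baseline items. If they differ, weight the one-year results for participation.
4. For the cohort, replace *unselected* with *consenting, internet-connected*.
5. Reconcile the statement that eligibility is the same in both studies with the consent and internet criteria.

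Early wound failure should not be restricted to events after consent. That would discard early failures already recorded, and it would not cure selection that depends on the state of the wound.

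The cost is mainly wording and a little more analysis, since the audit already collects the clinician data. The protocol says that consent is documented in REDCap but does not say that its date is kept, so this needs confirming. Weighting would widen the one-year intervals slightly.
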